The study design is shown in [Figure 1](#) below. The schedule of assessments is detailed in [Table 3](#).

The study includes 3 cohorts and approximately 36 participants will be enrolled. In each cohort, approximately 12 participants will be randomized to receive either INCB054707 (n = 9) or placebo (n = 3). The total duration of therapy for all enrolled participants is 8 weeks with a 30-day safety follow-up period. Cohort progression will be determined by the SRC evaluation of safety data following completion of Week 4 of all participants from a cohort (see Section [6.5.2](#)).

Table 3: Schedule of Assessments

Evaluation	Section	Screening	Treatment						Safety Follow-Up
		Day -28 to -1	Day 1 ^a	Week 1 ± 1 day	Week 2 ^b ± 3 days	Week 4 ^a ± 3 days	Week 6 ^b ± 3 days	Week 8 ^a ± 3 days (EOT)	
Administrative/screening procedures									
Informed consent	8.1.1	X							
Demography/medical history	8.1.6	X							
Inclusion/exclusion criteria	5	X	X						
Prior/concomitant medications	6.7	X	X	X	X	X	X	X	X
Serology	8.3.5.2	X							
Urinalysis	8.3.5.2	X							X
TB screening	8.3.5.2	X							
FSH ^c	8.3.5.2	X							
Pregnancy testing ^d	8.3.5.3	X	X	X	X	X	X	X	X
Contact IWRS	8.1.3	X	X	X	X	X	X	X	
Randomization to treatment arm	8.1.3		X						
Dispense study drug	6.1		X			X			
Collect study drug and assess compliance	6.4			X	X	X	X	X	
Distribute reminder cards	8.1.4	X	X	X	X	X	X	X	
Electronic diary verification	8.1.5		X	X	X	X	X	X	X
Safety procedures/assessments									
Comprehensive physical examination ^e	8.3.2	X						X	
Targeted physical examination	8.3.2		X	X	X	X	X		X
Vital signs	8.3.3	X	X	X	X	X	X	X	X
Hematology and chemistry assessments ^f	8.3.5.1, 8.6	X	X	X	X ^f	X ^f	X ^f	X	X
Lipid panel	8.3.5.1		X						X
CRP	8.3.5.1		X						X
12-lead ECG (screening) ^g	8.3.4	X							
12-lead ECG (predose and postdose) ^g	8.3.4		X			X			
12-lead ECG (predose only) ^g	8.3.4							X	
Assess AEs	8.3.1, 9	X	X	X	X	X	X	X	X

Table 3: Schedule of Assessments (Continued)

Evaluation	Section	Screening	Treatment						Safety Follow-Up
		Day -28 to -1	Day 1 ^a	Week 1 ± 1 day	Week 2 ^b ± 3 days	Week 4 ^a ± 3 days	Week 6 ^b ± 3 days	Week 8 ^a ± 3 days (EOT)	
Efficacy assessments									
Hurley Stage	8.2.1	X						X	X
AN count (HiSCR)	8.2.2	X	X	X	X	X	X	X	X
Modified Sartorius score	8.2.3		X					X	X
Record rescue lesional treatment	8.2.4			X	X	X	X	X	X
HS Pain NRS ^c	8.2.5		X	X	X	X	X	X	X
Evaluate daily analgesic use	8.2.6		X	X	X	X	X	X	X
HS-PGIC	8.2.7			X	X	X	X	X	X
DLQI	8.2.8		X	X	X	X	X	X	X

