Optional photography (target area)	8.2.9		X			X		X	

^a An overnight (at least 8-hour) fast will be required at these visits. Participant will take study drug at the study sites.

^b Participants will take study drug before the study visit.

^c For confirmation of nonchildbearing status for women who are postmenopausal, defined as amenorrhea at least 12 months before screening.

^d For women of childbearing potential only. Serum test will be conducted at screening and urine test will be conducted at all other visits.

^e A brief neurological examination will also be performed.

^f If there is a potential clinically significant abnormality in chemistry or hematology assessments (particularly in platelet count) at Week 2, 4, or 6, then an unscheduled visit the following week (Weeks 3, 5, 7) to repeat the assessment is required.

^g See [Table 10](#).

^h The HS Pain NRS includes worst pain and average pain in the last 24 hours.

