8.1.4. Distribution of Reminder Cards

Participants will be provided with a reminder card at the visits indicated at [Table 3](#). The reminder card will indicate the date/time of the next visit and will also remind the participant that they should not take study drug on Day 1, Week 4, and Week 8 as they will take it after blood draws for safety evaluation have been completed.

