8.3.5. Laboratory Assessments

8.3.5.1. Safety Assessments

Required laboratory tests are listed in Table 11. Safety laboratory tests include hematology, chemistry, CRP, and lipid panel (see Table 3). Participants may have a light snack before these visits but should allow for an overnight fast (at least 8 hours) before sample collection for the lipid panel.

If there is a potential clinically significant abnormality in hematology or chemistry assessments (particularly in platelet count) at Weeks 2, 4 or 6, then an unscheduled visit the following week (Weeks 3, 5, 7; see Section 8.6) to repeat laboratory assessments is required.

Clinical laboratory tests will be performed at a central laboratory (refer to the Laboratory Manual for sample handling and shipping instructions).

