8.8. Safety Follow-Up

The safety follow-up period is the interval between the EOT visit and the scheduled safety follow-up visit, which should occur 30 to 35 days after the EOT visit (or after the last dose of study drug if the EOT visit was not performed). Adverse events and SAEs must be reported up until the end of the safety follow-up period, the date of the follow-up visit, or until toxicities resolve, return to baseline, or are deemed irreversible, whichever is longer. Reasonable efforts should be made to have the participant return for the follow-up visit and report any AEs that may occur during this period.

For purposes of analysis, participants who complete through Week 8 will be considered to have completed the study.

9. ADVERSE EVENTS: DEFINITIONS AND PROCEDURES FOR RECORDING, EVALUATING, FOLLOW-UP, AND REPORTING

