8.1. General Considerations

Summary tables may be replaced with listings when appropriate. For instance, an AE frequency table may be replaced with a listing if it only contains a few unique preferred terms reported on relatively few participants.

Unless otherwise stated, table summaries will be limited to AEs occurring within 30 days of the last administration of study drug.

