8.3.2. Laboratory Value Summaries

Clinical laboratory tests, including hematology, serum chemistry, urinalysis, lipid panel, serology, C-reactive protein, follicle-stimulating hormone, serum pregnancy test, urine pregnancy test, and QuantiFERON-TB Gold test (refer to Protocol Table 11), will be performed for each participant during the study in accordance with study schedule of assessments (refer to Protocol Table 3). If specific safety issues arise, additional unscheduled laboratory tests/analyses may be performed at the discretion of the investigator.

All test results and associated normal ranges from central laboratories will be reported in SI units. All tests with numeric values will have a unique unit per test. Any laboratory test results and associated normal ranges from local laboratories will be converted to SI units. For the limited number of cases where the associated normal ranges from a local laboratory cannot be obtained despite due diligence, associated central laboratory normal ranges will be applied. In the event that central laboratory normal ranges are not available, a set of standard normal ranges based upon documented reference ranges will be applied to facilitate reporting the test results.

When there are multiple laboratory nonmissing values for a participant's particular test within a visit window, the smallest laboratory sequence number will be used to identify the record for postbaseline visits.

Laboratory parameters identified in Protocol Table 11 will be summarized. Shift tables based on worst postbaseline value recorded will use all postbaseline values occurring within 30 days of stopping study treatment. Other laboratory parameters collected will only be listed in an appendix to the CSR in their original units without SI conversions.

Actual values and changes from baseline in clinical laboratory test results will be summarized using descriptive statistics. Laboratory test values outside the normal range will be assessed for severity based on the normal ranges for the clinical reference laboratory. The incidence of abnormal laboratory values will be tabulated.

Laboratory data will be classified into Grades 1 through 5 using CTCAE v4.03. The following summaries will be produced for the laboratory data:

- Number and percentage of participants with worst postbaseline CTCAE grade (regardless of baseline value). Each participant will be counted only for the worst grade observed postbaseline.

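### The SAP closes AE tables and laboratory shift tables 30 days after the last dose, but the safety follow-up visit is due 30 to 35 days after EOT, so for completers only a day-30 sample enters the shift tables

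*SAP*

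**What the plan says.** **Analysis cut.** On laboratory data, SAP 8.3.2 says: "Shift tables based on worst postbaseline value recorded will use all postbaseline values occurring within 30 days of stopping study treatment". On adverse events, SAP 8.1 says: "Unless otherwise stated, table summaries will be limited to AEs occurring within 30 days of the last administration of study drug". The list of AE summaries in SAP 8.2.2 gives no other window.

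**Data collection.** Protocol 8.8 places the follow-up visit "30 to 35 days after the EOT visit (or after the last dose of study drug if the EOT visit was not performed". It requires AE reporting to the end of that period, "the date of the follow-up visit, or until toxicities resolve, return to baseline, or are deemed irreversible, whichever is longer". In Protocol Table 3 the row "Hematology and chemistry assessments" is marked at Weeks 1, 2, 4, 6 and 8 and again at safety follow-up.

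**Last dose in completers.** The Week 8 (EOT) column of Protocol Table 3 carries footnote a: "Participant will take study drug at the study sites". The reminder card in Protocol 8.1.4 tells participants that "they should not take study drug on Day 1, Week 4, and Week 8 as they will take it after blood draws". The Week 8 dose is therefore taken at the EOT visit.

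**Protocol analysis.** Protocol Table 14 analyses treatment-emergent AEs and shifts from baseline to the worst postbaseline value, with no day limit on either. SAP 2.1 says the SAP rests on Protocol Amendment 1. SAP 10.1 marks changes to protocol-defined analyses as not applicable.

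**The concern.** Safety is the only primary objective. The protocol asks every participant to return for a last blood draw and AE review, yet the earliest permitted day for that visit is also the last day that the SAP tables accept. Whether the sample counts in the worst-value tables then depends on how the visit was booked, not on anything clinical.

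The values at stake are relevant ones: Protocol 9.5 names platelet decreases and low ANC as events of special interest, and both are hematology results. With about 9 participants per dose, one participant is about 11% of a group (1/9).

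Two matters of consistency follow. The SAP narrows what Protocol Table 14 describes without recording it as a change. And the count of worst postbaseline CTCAE grade in SAP 8.3.2 carries no day limit, while the shift tables described beside it do, so one participant could show different worst grades in the two displays.

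**Working it through.** The documents give no figure on this point to reproduce. Their one computable design figure, the chance of at least one event among 9 participants at a 20% rate, does reproduce (1 − 0.8^9 = 0.866, stated as above 85%), but nothing here depends on it.

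**Inputs**
- Cut: 30 days after the last dose (SAP 8.1, 8.3.2).
- Permitted follow-up days: 30, 31, 32, 33, 34, 35 after EOT, so 6 days (Protocol 8.8).
- Gap from last dose to EOT: 0 days for completers (Protocol Table 3 footnote a; Protocol 8.1.4).
- Convention (assumed): days are date differences, and day 30 itself counts as within 30 days.

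**Rule.** Follow-up day after last dose = visit day after EOT + gap. The sample enters the shift tables if the result is at most 30.

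| Gap (days) | Follow-up days after last dose | Days inside the cut |
|---|---|---|
| 0 (completers) | 30 to 35 | 1 of 6 (16.7%) |
| 1 (assumed) | 31 to 36 | 0 of 6 |

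**Tables affected.** The SAP Appendix A shift tables are 3.3.2 and 3.3.3 (hematology) and 3.3.5 and 3.3.6 (chemistry). The sample in question is 1 of 6 scheduled postbaseline samples: Weeks 1, 2, 4, 6, 8 and follow-up.

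**Samples excluded.** Booking days are not given. Per dose level of 9 completers, the number excluded is 9 × (1 − P), where P is the share of visits on day 30. It runs from 0 of 9 (all on day 30) to 9 of 9 (none on day 30). If visits were spread evenly over the six days (an assumption), 27/6 = 4.5 of 27 follow-up samples on active drug would be kept, or 36/6 = 6 of 36 overall.

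**AE days excluded.** For a completer seen on day k, k − 30 onset days fall outside: 0 to 5, at most 5/35 = 14.3% of the post-dose days observed. With a gap of one day the range is 1/31 = 3.2% to 6/36 = 16.7%.

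These are counts of samples and days. They do not say how many table entries would differ.

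**The case against.** The strongest reply is that this is a deliberate and common window. The same 30 days appear in SAP 4.1.4, 8.1 and 8.3.2, and both documents describe follow-up as lasting 30 days. A fixed cut gives equal post-dose time, which suits worst-value tables. The excluded samples are all more than 30 days off drug. Nothing is discarded: SAP 8.2.1 keeps every AE in the listings, and the by-visit laboratory summaries in SAP 8.3.1 have no such cut. Unscheduled samples up to day 30 still count, and dose escalation uses Week 4 or Week 8 data.

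Most of this stands, and it is why the effect is modest. It does not remove the mismatch. Protocol 8.8 defines the follow-up period by a visit at days 30 to 35, Protocol Table 14 has no cut, and SAP 10.1 does not declare one.

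A reader might infer two further things that the documents do not support:
- That SAP 8.3.2 leaves open whether the follow-up sample counts, because its percentage sentence refers to the treatment period. That sentence concerns denominators. The date rule settles the matter: a value within 30 days counts, a later one does not.
- That lipid panel and CRP lose their only scheduled postbaseline value. SAP Appendix A plans shift tables only for hematology and chemistry, and the schedule rows on which this reading rests may not have been extracted correctly.

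**Conclusion.** The mismatch is real and lies in current text. For completers, 1 of 6 permitted follow-up days gives a sample that enters the hematology and chemistry shift tables, and up to five days of AE onset are collected but not tabulated. This rests on the last dose falling on the EOT day, which the protocol supports, and on counting day 30 as inside. For anyone whose EOT visit comes after the last dose, no follow-up day permitted by Protocol 8.8 qualifies.

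It would be wrong to conclude that safety data are lost or that the primary assessment is unsound. On-treatment values and values to day 30 off drug are all in the tables. What is missing is limited to the latest observations, and its effect on the tables cannot be computed from the documents. The change is worth making because it is cheap and bears on the primary objective.

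Separately, Protocol 7.1.2 counts follow-up for participants who discontinue as the discontinuation date plus 30 days, while Protocol 8.8 gives 30 to 35 days after EOT. The two must be reconciled.

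**What to change.** In SAP 8.1 and 8.3.2, replace the 30-day limit with one fixed limit matching the protocol window: from first dose through 35 days after the EOT visit, or after the last dose if no EOT visit took place. Apply it by onset date for AEs and by sample date for laboratory values, so that the open-ended follow-up of toxicities in Protocol 8.8 does not stretch it. Keep it fixed even when the visit is attended late.

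Counting from EOT matters. It includes all 6 permitted days whatever the gap, whereas 35 days counted from the last dose would include 5 of 6 with a one-day gap and 4 of 6 with a two-day gap.

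Apply the same limit to the worst postbaseline CTCAE grade count, and record the limit in SAP 10.1.

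**Cost.** A few SAP sentences, the 10.1 entry and one programming window. A few off-drug values and late AEs will enter the tables, and post-dose observation will differ by a few days between participants (30 to 35 for completers with an on-time visit, longer if EOT follows the last dose). A 30-day version can be kept as a supplementary table for the equal-time view. Reconciling Protocol 7.1.2 with 8.8 is a separate change to the protocol text.

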8.4. Vital Signs

Values at each scheduled visit, change, and percentage change from baseline for vital signs, including systolic blood pressure, diastolic blood pressure, pulse, body temperature, and respiratory rate will be summarized descriptively.

Criteria for clinically notable vital sign abnormalities are defined in [Table 4](#). The abnormal values for participants exhibiting clinically notable vital sign abnormalities will be listed. Alert vital signs are defined as an absolute value outside the defined range and percentage change greater than 25%. The abnormal values for participants exhibiting alert vital sign abnormalities will be listed.

Table 4: Criteria for Clinically Notable Vital Sign Abnormalities

Parameter	High Threshold	Low Threshold
Systolic blood pressure	> 155 mmHg	< 85 mmHg
Diastolic blood pressure	> 100 mmHg	< 40 mmHg
Pulse	> 100 bpm	< 45 bpm
Temperature	> 38°C	< 35.5°C
Respiratory rate	> 24 breaths/min	< 8 breaths/min

8.5. Electrocardiograms

All 12-lead ECGs will be performed as indicated in [Table 5](#) with the participant in a recumbent or semirecumbent position after at least 5 minutes of rest. Additional 12-lead ECGs may be performed at other visits as deemed clinically necessary. Electrocardiograms will be interpreted by the investigator at the site, and the results will be used for immediate management of the participant's care. The decision to include or exclude a participant or withdraw a participant from the study based on an ECG flagged as "Abnormal, Clinically Significant" is the responsibility of the investigator, in consultation with the sponsor's medical monitor, as appropriate. Any abnormalities that are considered clinically significant in the judgment of the investigator are to be reported as AEs.

Descriptive statistics and mean change from baseline will be determined for each ECG parameter at each assessment time. Change and percentage change from baseline will be calculated. Triple ECGs will be measured at baseline and postbaseline visits if necessary. Electrocardiogram abnormalities, both at baseline and postbaseline visits, will be tabulated. Incidences of abnormalities will be listed with study visit, and a description of the abnormality.

Table 5: Electrocardiogram Schedule

Study Visit	Timing of Electrocardiogram Relative to Administration of Study Drug		
	Not Applicable	Predose (Trough) ECG ^a	Postdose (Postdose 2) ECG ^b
Screening ^c	Single → Triple ^d		
Day 1		Triple ^e	Single → Triple ^d
Week 4		Single → Triple ^d	Single → Triple ^d
Week 8		Single → Triple ^d	

^a Predisose ECG should be performed 5 to 10 minutes before the predisose [REDACTED].

^b Postdose ECGs will be performed after participants complete all of the study assessments but before the collection of the second postdose (postdose 2) [REDACTED]. Postdose ECG will be measured 5 to 10 minutes before the postdose (postdose 2) [REDACTED] collection.

^c Prolonged QTcF values of ≥ 450 ms at screening are to be confirmed by performing 2 additional ECGs and averaging the results to determine whether the averaged value meets the exclusion criterion.

^d Single → Triple: Single ECG will be performed first. If prolonged QT interval (corrected for heart rate using Fridericia's formula [QTcF], defined as ≥ 450 ms) are observed, an additional 2 ECGs will be measured within the next 5 minutes.

^e Day 1 predisose ECG will be performed in triplicate, and values will be averaged to calculate the baseline values.

9. INTERIM ANALYSES

No formal interim analysis is planned in this study.

10. CHANGES AND MODIFICATIONS TO THE ANALYSIS PLAN

All versions of the SAP are listed in [Table 6](#).

Table 6: Statistical Analysis Plan Versions

SAP Version	Date
Original	01 MAR 2019

10.1. Changes to Protocol-Defined Analyses

Not applicable.

10.2. Changes to the Statistical Analysis Plan

Not applicable.

APPENDIX A. PLANNED TABLES, FIGURES, AND LISTINGS

This appendix provides a list of the planned tables, figures, and listings for the CSR. Shells are provided for nonstandard tables in a separate document. In-text tables are identical in structure and content as appendix tables, but follow a Rich Text Format.

The lists of tables, figures, and listings are to be used as guidelines. Modifications of the lists that do not otherwise affect the nature of the analysis will not warrant an amendment to the SAP.

Tables

Table No.	Title	Population
Baseline and Demographic Characteristics		
1.1 Disposition		
1.1.1	Analysis Populations	FAS
1.1.2	Summary of Participant Disposition	FAS
1.1.3	Summary of Number of Participants Enrolled By Site	FAS
1.2 Demography		
1.2.1	Summary of Demographics	FAS
1.3 Baseline Characteristics		
1.3.1	Summary of Baseline Disease Characteristics	FAS
1.4 Prior Medication and Concomitant Medication		
1.4.1	Summary of Prior Medications	FAS
1.4.2	Summary of Prior Medications for Hidradenitis Suppurativa	FAS
1.4.3	Summary of Concomitant Medications	FAS
1.5 Others		
1.5.1	Summary of General Medical History	FAS
1.5.2	Summary of Protocol Deviations	FAS
Efficacy		
2.1.1	Summary of Participants With a HiSCR by Visit	FAS
2.1.2	Summary of Participants Achieving an AN Count of 0 to 2 by Visit	FAS
2.1.3.1	Summary of HS Pain NRS Score From Baseline to End of Study (Worst Pain)	FAS
2.1.3.2	Summary of HS Pain NRS Score From Baseline to End of Study (Average Pain)	FAS
2.1.4	Summary of Modified Sartorius Scale Score From Baseline to Week 8	FAS
2.1.5	Summary of Draining Fistulas Count From Baseline to End of Study	FAS
2.1.6.1	Summary of Hurley Stage at Baseline and Week 8	FAS
2.1.6.2	Summary of Hurley Stage Change From Baseline to Week 8	FAS
2.1.7	Summary of HS-PGIC Category by Visit	FAS
2.1.7.1	Summary of HS-PGIC by Visit	FAS
2.1.8	Summary of Participants Requiring Rescue Lesional Treatment by Visit	FAS
2.1.9	Summary of Interventions With Rescue Lesional Treatment by Visit	FAS
2.1.10.1	Summary of DLQI Category by Visit	FAS
2.1.10.2	Summary of DLQI Score From Baseline to End of Study	FAS
2.1.13	Summary of Daily Analgesic Usage	FAS

Table No.	Title	Population
Safety		
3.1 Study Drug Exposure		
3.1.1	Summary of Drug Compliance	FAS
3.1.2	Summary of Study Drug Exposure	FAS
3.2 Adverse Events		
3.2.1	Overall Summary of Treatment-Emergent Adverse Events	FAS
3.2.2	Summary of Treatment-Emergent Adverse Events by MedDRA System Organ Class and Preferred Term	FAS
3.2.3	Summary of Treatment-Emergent Adverse Events by MedDRA Preferred Term in Decreasing Order of Frequency	FAS
3.2.4	Summary of Treatment-Emergent Adverse Events by MedDRA System Organ Class, Preferred Term, and Maximum Severity	FAS
3.2.5	Summary of Grade 3 or Higher Treatment-Emergent Adverse Events by MedDRA System Organ Class and Preferred Term	FAS
3.2.6	Summary of Treatment-Related Adverse Events by MedDRA System Organ Class and Preferred Term	FAS
3.2.7	Summary of Treatment-Related Adverse Events by MedDRA Preferred Term in Decreasing Order of Frequency	FAS
3.2.8	Summary of Treatment-Related Adverse Events by MedDRA System Organ Class, Preferred Term, and Maximum Severity	FAS
3.2.9	Summary of Grade 3 or Higher Treatment-Related Treatment-Emergent Adverse Events by MedDRA Preferred Term	FAS
3.2.9.1	Summary of Grade 3 or Higher Treatment-Emergent Adverse Events by Preferred Term in Decreasing Order of Frequency	FAS
3.2.10	Summary of Treatment-Emergent Adverse Events Leading to Death by MedDRA System Organ Class and Preferred Term	FAS
3.2.11	Summary of Serious Treatment-Emergent Adverse Events by MedDRA System Organ Class and Preferred Term	FAS
3.2.12	Summary of Serious Treatment-Emergent Adverse Events by MedDRA Preferred Term in Decreasing Order of Frequency	FAS
3.2.13	Summary of Treatment-Related Serious Treatment-Emergent Adverse Events by MedDRA System Organ Class and Preferred Term	FAS
3.2.14	Summary of Treatment-Emergent Adverse Events Leading to Dose Interruption by MedDRA System Organ Class and Preferred Term	FAS
3.2.15	Summary of Treatment-Emergent Adverse Events Leading to Discontinuation of Treatment by MedDRA System Organ Class and Preferred Term	FAS
3.2.16	Summary of Nonserious Treatment-Emergent Adverse Events by MedDRA System Organ Class and Preferred Term	FAS
